**Study Endpoints:****1- Primary effectiveness endpoint:**

- Study success defined as adequate short-term drainage defined as the presence of the stent in the ureter and the lack of surgical or other intervention to treat symptoms associated with the stent itself on the stented side during the first 48 hours [Day 0-2] following placement.
- [Note: In some cases, the ureteral stent may not be sufficient to relieve pain (not associated with stent specifically) and alternative surgical treatment may be warranted. In these cases, patient data will be captured but non-device related cause captured as reason for subject stenting termination.]
- Assessment of retrograde urine reflux after placement of the ureteral stent, as determined by the visualization of urine in the distal ureter to the kidney using cystography after contrast gravity-filling of the bladder and assigning a urinary reflux grade based on:
  - Grade I: urine refluxes into the ureter only.
  - Grade II: urine refluxes into the ureter and up to the kidney without dilation.

- Grade III: urine refluxes into the ureter and kidney and causes mild dilation.
- Grade IV: urine refluxes into ureter and kidney and causes dilation without twisting of the ureter.
- Grade V: urine refluxes into ureter and kidney and causes significant dilation with twisting of the ureter.

- Visualization of distal coil in bladder, after stent placement. Document placement using a cystoscope.

2- Primary safety endpoint:  
Assessment of pain or irritative symptoms (incidence, severity) attributed to the ureteral stent as well as unplanned return visits to ED, OR, or clinic.

3- Secondary endpoint:

- USSQ Scale (Ureteral Stent Symptoms Questionnaire) [Time Frame: Day 3 as endpoint]
- Unplanned hospital visits or doctor visits related to the stent
- Medication use endpoint:
  - Physicians can prescribe standard medications such as alpha blocker (Tamsulosin), Anticholinergic (Oxybutynin), phenazopyridine (Pyridium), ibuprofen and Tylenol prn pain for the duration of the stent plus 1 day (post stent removal) (Document on CRF)
  - Requests for “breakthrough” pain medication (narcotics) would be at the request of the patient post procedure (not to be given as a standard dose). (Document on CRF)
  - Patients to keep medication diary in situations where patients are not taking medications as prescribed
  - Use of medication (amount and type of medication) will be analyzed between the RELIEF stent and DJ Stent groups, including calculation of cost of medications between 2 groups

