### 1.1 SYNOPSIS

**Title:** The RELIEF Ureteral Stent vs. Standard DJ Stent – Assessment of Retrograde Urinary Reflux

**Study Description:** Assessment of retrograde urine reflux after placement of the RELIEF® Ureteral Stent using cystography after contrast gravity-filling of the bladder and assigning a urinary reflux grade.

Randomized controlled trial for evaluation of the stent placement and the adequacy of short-term drainage (defined as the presence of the stent in the ureter and the lack of surgical or other intervention to treat symptoms associated with the stent itself on the stented side during the first 48 hours).

**Primary Objective:** Assessment of retrograde urine reflux after placement of a ureteral stent using cystography after contrast gravity-filling of the bladder and assigning a urinary reflux grade based on standard scoring.

**Secondary Objectives:** Assessment of stent symptoms (incidence, relationship to device, severity) attributed to the ureteral stent; Reporting the Ureteral Stent Symptoms Questionnaire (USSQ) before stent placement, after placement at day 3, prior to removal and post removal; Visualization of distal coil floating in bladder (Y/N) after stent placement

**Primary Endpoint:** Study success defined as adequate short-term drainage defined as the presence of the stent in the ureter and the lack of surgical or other intervention to treat symptoms associated with the stent itself on the stented side during the first 48 hours [Day 0-2] following placement.

**Secondary Endpoints:** USSQ Scale (Ureteral Stent Symptoms Questionnaire) [Time Frame: Day 3 as endpoint, Unplanned hospital visits or doctor visits related to the stent, Medication use

**Description of Sites/Facilities Enrolling Participants:** UC San Diego

**Description of Study Intervention:** Randomized Controlled Trial

**Study Duration:** 1 year

**Participant Duration:** 1 year

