### 2.3.2 KNOWN POTENTIAL BENEFITS

There is potential direct benefit for the patients assigned to the RELIEF stent group as we suspect it will provide relief from discomfort during recovery after ureteroscopy. The knowledge to be gained from this research is whether the Relief stent reduces urinary reflux and decreases postoperative pain and discomfort for patients who undergo kidney stone surgery and stent placement. If the Relief stent provides improvement in symptoms, this will improve patient care and comfort.

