## 4 STUDY DESIGN

### 4.1 OVERALL DESIGN

Allocation: Randomized 1:1 RELIEF stent vs. DJ Stent

Endpoint Classification: Comparison Study

Intervention Model: Two Group Assignment

Masking: Open Label

Primary Purpose: Treatment

Patients will undergo their scheduled ureteroscopy with laser lithotripsy and ureteral stent placement per standard of care methods.

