## 6.3 MEASURES TO MINIMIZE BIAS: RANDOMIZATION AND BLINDING

Patients will be randomized to receive either the Relief stent or the standard ureteral stent. The randomization sequence will be computer-generated, and patients will be randomly allocated based on this sequence.

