### 8.3.3.2 RELATIONSHIP TO STUDY INTERVENTION

All adverse events (AEs) must have their relationship to study intervention assessed by the clinician who examines and evaluates the participant based on temporal relationship and his/her clinical judgment. The degree of certainty about causality will be graded using the categories below. In a clinical trial, the study product must always be suspect.

- **Definitely Related** – There is clear evidence to suggest a causal relationship, and other possible contributing factors can be ruled out. The clinical event, including an abnormal laboratory test result, occurs in a plausible time relationship to study intervention administration and cannot be explained by concurrent disease or other drugs or chemicals. The response to withdrawal of the study intervention (DE challenge) should be clinically plausible. The event must be pharmacologically or phenomenologically definitive, with use of a satisfactory rechallenge procedure if necessary.
- **Probably Related** – There is evidence to suggest a causal relationship, and the influence of other factors is unlikely. The clinical event, including an abnormal laboratory test result, occurs within a reasonable time after administration of the study intervention, is unlikely to be attributed to concurrent disease or other drugs or chemicals, and follows a clinically reasonable response on withdrawal (dechallenge). Rechallenge information is not required to fulfill this definition.
- **Potentially Related** – There is some evidence to suggest a causal relationship (e.g., the event occurred within a reasonable time after administration of the trial medication). However, other factors may have contributed to the event (e.g., the participant's clinical condition, other concomitant events). Although an AE may rate only as "possibly related" soon after discovery, it can be flagged as requiring more information and later be upgraded to "probably related" or "definitely related", as appropriate.
- **Unlikely to be related** – A clinical event, including an abnormal laboratory test result, whose temporal relationship to study intervention administration makes a causal relationship improbable (e.g., the event did not occur within a reasonable time after administration of the study intervention) and in which other drugs or chemicals or underlying disease provides plausible explanations (e.g., the participant's clinical condition, other concomitant treatments).

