#### 8.3.4 TIME PERIOD AND FREQUENCY FOR EVENT ASSESSMENT AND FOLLOW-UP

The occurrence of an adverse event (AE) or serious adverse event (SAE) may come to the attention of study personnel during study visits and interviews of a study participant presenting for medical care, or upon review by a study monitor.

All AEs including local and systemic reactions not meeting the criteria for SAEs will be captured on the appropriate case report form (CRF). Information to be collected includes event description, time of onset, clinician's assessment of severity, relationship to study product (assessed only by those with the training and authority to make a diagnosis), and time of resolution/stabilization of the event. All AEs occurring while on study must be documented appropriately regardless of relationship. All AEs will be followed to adequate resolution.

Any medical condition that is present at the time that the participant is screened will be considered as baseline and not reported as an AE. However, if the study participant's condition deteriorates at any time during the study, it will be recorded as an AE.

Changes in the severity of an AE will be documented to allow an assessment of the duration of the event at each level of severity to be performed. AEs characterized as intermittent require documentation of onset and duration of each episode.

The study coordinator will record all reportable events with start dates occurring any time after informed consent is obtained until 7 (for non-serious AEs) or 30 days (for SAEs) after the last day of study participation. At each study visit, the investigator will inquire about the occurrence of AE/SAEs since the last visit. Events will be followed for outcome information until resolution or stabilization.

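### The symptom part of the primary safety endpoint counts only symptoms attributed to the stent, in an open-label trial with no attribution rule, so differences in attribution can create or hide a difference between arms

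*Combined protocol and SAP*

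**What the plan says.** Section 3 gives the primary safety endpoint as "Assessment of pain or irritative symptoms (incidence, severity) attributed to the ureteral stent", together with unplanned returns to the emergency department, operating room or clinic. The Synopsis (1.1) lists the same assessment as a secondary objective, "Assessment of stent symptoms (incidence, relationship to device, severity) attributed to the ureteral stent", and the secondary objectives in Section 3 carry the same limit to stent-attributed symptoms.

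Section 4.1 states "Masking: Open Label" and has every patient undergo ureteroscopy with laser lithotripsy together with stent placement. Section 6.3, on randomization and blinding, describes only the sequence: "The randomization sequence will be computer-generated, and patients will be randomly allocated based on this sequence". It mentions no masked assessor or adjudicator.

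No section says who attributes a symptom for this endpoint, or by what rule. The nearest text is Section 8.3.3.2, where the relationship of an adverse event to the intervention is "assessed by the clinician who examines and evaluates the participant based on temporal relationship and his/her clinical judgment". Section 4.1 has study personnel evaluate tolerability at follow-up, in person or by phone. Section 8.3.4 adds that "All AEs occurring while on study must be documented appropriately regardless of relationship". On RELIEF, Section 2.3.2 expects direct benefit, "as we suspect it will provide relief from discomfort during recovery after ureteroscopy".

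**The concern.** A symptom enters the endpoint only after someone has decided that the stent, rather than the operation, caused it. Both happened in the same session, so timing cannot separate them. The decision is made after randomization and, as far as the plan shows, by someone who can know the arm. The same flank pain could be recorded as stent-related in one arm and surgical in the other.

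Randomization already balances surgical symptoms in expectation, so the filter is not needed for a fair comparison of the stents, and it opens a route for bias. At stake is the between-arm reading of symptom incidence and severity, which bears on the second benefit hypothesized in Section 3, fewer irritative bladder symptoms.

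**Working it through.** **The plan's own figure.** The only power statement (4.2 and 9.2) concerns reflux incidence: N = 50, w = 0.4, alpha 0.05, power 80%. The noncentrality is N × w² = 50 × 0.16 = 8, and the 1-df chi-square then has power 80.7%. The figure reproduces, but it says nothing about the safety endpoint.

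**Inputs for the illustration.**
- 25 patients per arm (9.2).
- True symptom incidence of 80% in both arms. This is the upper figure for stented patients in 2.2, taken here as an assumption.
- Probability that a symptom is attributed to the stent: an assumption throughout, because the documents give none.
- Test: two-sided chi-square or Fisher at 0.05. Section 9.4 names these for reflux and for categorical USSQ findings, not for this endpoint, so this too is an assumption.

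**Formula.** Scored rate = true incidence × attribution probability. For example, DJ 0.80 × 0.95 = 0.76 and RELIEF 0.80 × 0.70 = 0.56. The chance of p<0.05 with RELIEF lower is the sum of the two binomial probabilities (n = 25 each) over all tables that meet that condition.

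| Attribution, DJ / RELIEF | Scored, DJ / RELIEF | Chi-square | Fisher |
|---|---|---|---|
| 90% / 90% | 72% / 72% | 2.7% | 1.1% |
| 95% / 90% | 76% / 72% | 5.4% | 2.4% |
| 95% / 85% | 76% / 68% | 9.6% | 4.8% |
| 95% / 80% | 76% / 64% | 15.6% | 8.7% |
| 95% / 70% | 76% / 56% | 33.8% | 22.8% |

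At 60% true incidence, the last two rows become 57% / 48% (11.3%, 6.7%) and 57% / 42% (21.7%, 14.1%).

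**Direction.** The calculation is symmetric: exchanging the arms gives the same probabilities in favour of DJ. If symptoms were blamed more readily on RELIEF, a true advantage of RELIEF would shrink or disappear.

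**Without a test.** The scored difference is incidence × attribution gap. At 80% incidence, gaps of 5 to 25 points give 0.80 × 5 = 4 to 0.80 × 25 = 20 percentage points from labelling alone.

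**The case against.** - **The attributor is not named.** This stands. A reader might infer that unmasked staff make the call. That is plausible from 4.1 and 8.3.3.2, but the latter governs adverse events and the endpoint itself names nobody. If patients attribute, the plan does not mask them either. What is documented is an undefined and unmasked attribution step.
- **The direction is not settled.** This also stands. A reader might infer that the filter must favour RELIEF, given the optimism in 2.3.2. But 8.3.3.2 also tells clinicians to hold the study product under suspicion at all times, which could load more symptoms onto the research stent.
- **The filter itself is not quite clear.** The Synopsis lists relationship to device as something to record, which is largely redundant if only attributed symptoms enter. Yet the same line still restricts to symptoms attributed to the stent, as does Section 3.
- **Other comparisons carry the symptom hypothesis.** Largely true. The USSQ is completed by patients and compared by arm (9.4.3), medication use is compared by arm (Section 3), and 9.4.4 compares adverse events, which are recorded whatever their relationship. None of these carries the filter. They limit the damage but do not redefine the primary safety endpoint.
- **The gaps are assumed.** True. With gaps of 5 to 10 points the chance is only about 5–10% (chi-square) or 2–5% (Fisher).
- **Device safety endpoints often use attribution.** It can be kept as a description; it need not be the entry condition for the main comparison.

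**Conclusion.** The point holds as a design weakness: an unmasked judgment without a rule, made after randomization, decides which symptoms count, so the arms can differ on this endpoint without differing in symptoms, and a real difference can be hidden.

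The size is unknown. The 5–34% (chi-square) and 2–23% (Fisher) range rests on assumed attribution gaps of 5 to 25 points, 80% incidence, and a test that the plan does not name for this endpoint. It shows what is possible and is not an estimate. The documents do not show that biased scoring will occur, or that it would favour RELIEF.

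The reach is limited. Reflux, the only endpoint with a power statement, is unaffected, as are the USSQ and medication comparisons; no decision rule is attached to the safety endpoint. The change should be made because it is cheap and removes an avoidable source of bias.

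**What to change.** In the Synopsis (1.1) and in the secondary objectives and primary safety endpoint of Section 3:

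1. Define the main symptom comparison as all new or worsened pain or irritative urinary symptoms after stent placement, over a stated window, whatever the attributed cause, compared by randomized arm.
2. Use the pain and irritative items already named in 2.2: urgency, frequency, dysuria, incontinence, suprapubic discomfort and flank pain. Report hematuria and febrile infection separately as adverse events, since they are neither pain nor irritative symptoms.
3. Keep attribution to the stent as a descriptive column.

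**Cost.** Mostly wording, because 8.3.4 already records adverse events regardless of relationship. That section treats conditions present at screening as baseline unless they deteriorate, which is why the definition says new or worsened. Judging this needs each patient's symptom status before placement. Section 3 calls for a USSQ before placement, but the schedule in 1.3 shows none before Day 1, so one baseline entry would have to be scheduled. Surgical symptoms will enter both arms and dilute the contrast somewhat, by an amount the documents do not allow us to estimate. Open-label reporting bias remains; the change removes only the attribution step.

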## 3 OBJECTIVES AND ENDPOINTS

We hypothesize that the RELIEF stent will offer the same function as a traditional stent with the added benefits of 1) prevention of urinary reflux and 2) reduction of irritative bladder symptoms.

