#### Post-stent Follow-Up:

- Post-operatively complete Ureteral Stent Satisfaction Questionnaire (USSQ) surveys at day 1, day 3, day of stent removal, and 2 days post stent removal (note day of removal) (between 7-10 days in normal practice (even up to 14 days):
- Medications will be tracked on the CRF at day 1, day 3, day of stent removal, and 2 days post stent removal
- Day 1 (12-30 hours after stenting procedure), subject will be evaluated by study personnel for acceptable procedural outcome.
- Document any unplanned hospital visits or doctor visits related to the stent  
Day 1, Day 3, Day of stent removal (i.e., Day 7-10), and 2 days post stent removal, subject will be evaluated by study personnel for ongoing tolerability and stent performance (e.g., drainage) in person or by phone.
- Direct or remote evaluation will be documented. If unusual levels of pain or other potentially serious complications are suspected, the subject will be brought in for Clinician evaluation.

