# 8 STUDY ASSESSMENTS AND PROCEDURES

## 8.1 EFFICACY ASSESSMENTS

The primary objective of the study is to assess whether the Relief stent causes reflux of urine. This will be assessed using a standardized grading system described previously. The additional objective of evaluating adequacy of short-term drainage uses the following definition: presence of stent in the ureter and lack of surgical or other intervention to treat symptoms associated with the stent itself during the first 48 hours. This will be determined during the phone interview or in person visit with the patient on

days 1 and 3 as well as by questionnaire. Medications used will be tracked on the research form per the timeline at days 1, 3, 7-10.

Screening will occur in the clinics to identify patients with stone disease who meet eligibility requirements and who require surgical treatment for their stones.

Patients who are deemed clinically suitable and choose to participate will be screened utilizing the EMR for recruitment. The urology provider will first determine if they are interested in participating in the research study and upon agreement, a study team member or research coordinator will introduce the study details and initiate a consent interview. If eligible, these patients will be approached during pre-surgical preoperative clinic visits by the research team to further explain the study and further address any of their questions and get their consent. Patients will be free to leave the study without any impact or influence on their clinical care or management at any point should they desire to do so.

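### A medication diary is added only when patients depart from their prescription, so the completeness of recording behind the medication amount and cost comparison can differ by arm

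*Combined protocol and SAP*

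**What the plan says.** Medication use is listed as a secondary endpoint in the Synopsis (1.1) and in Section 3. Section 3 states the comparison: "Use of medication (amount and type of medication) will be analyzed between the RELIEF stent and DJ Stent groups", with medication cost calculated for the two groups as well.

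Two kinds of record feed it.

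- **CRF, all patients.** Section 4.1 (Post-stent Follow-Up): "Medications will be tracked on the CRF at day 1, day 3, day of stent removal, and 2 days post stent removal". The Schedule of Activities (1.3) agrees, with a medication review at each of these contacts. Section 8.1 gives a shorter list: "Medications used will be tracked on the research form per the timeline at days 1, 3, 7-10".
- **Diary, some patients.** Section 3: "Patients to keep medication diary in situations where patients are not taking medications as prescribed". This is the only sentence on a diary.

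Among the permitted drugs Section 3 names "ibuprofen and Tylenol prn pain for the duration of the stent plus 1 day" after removal. Narcotics for breakthrough pain are given only when the patient asks, with no standard dose. Both are to be documented on the CRF.

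The design is "Masking: Open Label" (4.1), and the Section 3 hypothesis expects RELIEF to bring "reduction of irritative bladder symptoms".

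**The concern.** Whether a patient has a diary in addition to the CRF depends on what the patient does after randomisation. Symptoms plausibly influence whether someone skips, stops or exceeds a drug, and the stent is expected to change symptoms. The proportion of patients with the extra record may therefore differ between arms because of the treatment, and randomisation does not protect against that. Patients and staff also know the assignment, and no section says who judges that the trigger has been met, when, or how use before the diary started is recovered.

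If the CRF alone and the CRF plus a diary do not count the same amount for the same true use, the arm difference in amount and cost mixes real consumption with completeness of recording. The two cannot be separated afterwards, because as-needed doses that were never written down cannot be retrieved.

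**Working it through.** **The plan's own figure.** The only statistical figure is the power for reflux incidence (4.2 and 9.2): N = 50, w = 0.4, alpha 0.05. Noncentrality is 50 × 0.4² = 8; with 1 df and critical value 3.84, power is 0.807, which reproduces the stated 80%. It does not concern medication use. The documents give no figure for that endpoint, and 9.4.3 names an analysis for the USSQ only.

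**Where adherence does and does not fix the amount.**

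- Fixed-schedule drug: a patient who takes it as prescribed has taken a known amount. Having no diary loses little.
- As-needed ibuprofen or Tylenol, and narcotics on request: a patient can take none or many doses and still be within the prescription. No diary is triggered, and the prescription does not reveal the amount.

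**Gap covered by the CRF alone.** Contacts fall on Day 1, Day 3, removal and two days after removal.

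- Removal on Day 7: 7 - 3 = 4 days since the last contact.
- Removal on Day 10: 10 - 3 = 7 days.
- Removal on Day 14, which 4.1 (Post-stent Follow-Up) and 7.1 allow for: 14 - 3 = 11 days.

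No section says how doses taken between contacts are counted without a diary, or how diary and CRF entries are combined.

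**Illustration (all values assumed).** Let mean true use be 1 in both arms, and the same for patients with and without a diary. Let the diary be accurate, and let CRF-only recording give c times true use. Let q be the share keeping a diary. The recorded mean in an arm is q + (1 - q)c, so the spurious difference, RELIEF minus DJ, is

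(c - 1) × (q_DJ - q_RELIEF).

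| q RELIEF | q DJ | c = 0.8 | c = 1.25 | c = 1.5 |
|---|---|---|---|---|
| 0.3 | 0.3 | 0 | 0 | 0 |
| 0.4 | 0.2 | +4% | -5% | -10% |
| 0.6 | 0.2 | +8% | -10% | -20% |

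For example, with 0.6 vs 0.2 and c = 1.5: 0.5 × (0.2 - 0.6) = -0.20. The sign depends on whether CRF-only recording under-counts (c < 1) or over-counts (c > 1). Exchanging the two diary shares reverses every sign.

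**Scale.** With 25 per arm, the difference detectable with 80% power at two-sided 0.05 is (1.96 + 0.8416) × √(2/25) = 0.79 SD (normal approximation). If the SD equals the mean (assumed), a spurious 10% is 0.1 SD and 20% is 0.2 SD; if the SD is half the mean, they are 0.2 and 0.4 SD. The artefact would more likely distort the estimate than create a significant result by itself.

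**The case against.** The strongest reply is that all patients in both arms have the CRF record at the same four contacts, and that 8.1 speaks of medications used, not prescribed. The contrast is CRF against CRF plus diary, not two unrelated methods. Moreover, the rule gives the diary to exactly those whose intake cannot be read from the prescription; everyone else took what was prescribed, so nothing is lost. The sentence can also be read as asking for a supplementary note of departures, since no section says diary data replace CRF data in the endpoint.

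Most of this stands for fixed-schedule drugs. It does not stand for as-needed drugs and narcotics, where being within the prescription leaves the amount open and the CRF-only patient is asked about several days at once.

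A reader might go further and infer that diary patients have daily records while the rest are reconstructed from the prescription, and that RELIEF will therefore show a false saving. The documents do not support this:

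- They give no frequency or format for the diary, and nowhere say that amounts are taken from the prescription.
- An example in which patients without a diary take only part of the prescribed amount but are recorded at all of it breaks the plan's own rule, because those patients should have had a diary.
- The direction is open. Patients with fewer symptoms may skip drugs, and those with more may exceed them; both would trigger a diary.

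**Conclusion.** The concern holds in a limited form. Recording intensity for a between-arm endpoint depends on post-randomisation behaviour that the stent may change, in an open-label trial. The weakness is confined mainly to as-needed ibuprofen and Tylenol and on-request narcotics, which can contribute materially to amount and cost.

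Neither size nor direction can be established from the documents. The range of +8% to -20% of true use rests on assumed diary shares and assumed recording ratios, and the bias is zero if the shares are equal or the two records count alike. Medication use is a secondary endpoint; the reflux comparison and its power statement are untouched. This is an inexpensive improvement worth making before enrolment, not a threat to the trial's main conclusion.

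**What to change.** In Section 3, replace the conditional diary sentence with one that applies to everyone: all participants in both arms keep the same medication diary from Day 0 to one day after stent removal, reviewed at each CRF contact. State that amount, type and cost are derived from that single source by the same rule in both arms, and give the rule, including how cost is calculated and how missing entries are handled.

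Separately, reconcile the tracking timepoints. Section 8.1 stops at Days 7-10, whereas 4.1 and the Schedule of Activities include the contact two days after removal. This is an inconsistency in its own right and is not evidence for the diary point, but the later contact is the one that can cover the last day of the medication window.

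The cost is a short form for 50 patients over about one to two weeks each, with a small added burden on patients. The change concerns measurement only and does not alter treatment.
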